3.2.2 SECONDARY TRIAL OUTCOME - POWERED DEPRESSION OUTCOME

AIM 2: Improvement in depressive symptoms. A reduction in depressive symptoms from the study qualifying PHQ score to follow-up PHQ score documented as part of routine clinical care 3-13 months later.

The analytical approach to handling the situation in which some individuals have multiple PHQ measures documented during the follow-up window will be specified in the statistical analysis plan (a brief overview of the methods considered and the general simulation approach to guide the choice of method is given in Supplement 3, part B).

Rationale: A prior study found a change between 2.59 and 4.78 to be the minimal clinically important difference (MCID), leading to a commonly defined threshold of 3-5 points for the MCID. However, no studies have evaluated the PHQ in patients with OUD. Therefore, we chose to not pre-define a specified threshold. In addition, we use the interval of 3-13 months to ensure 60% follow-up PHQ-9s based on preliminary studies showing that 13 months after randomization maximizes follow-up (likely due to EHR prompts at 12 months for repeat screening). (See Supplement 2 for additional rationale).

To get a fuller picture of changes in depressive symptoms we will also assess clinically significant improvement in depressive symptoms defined as at least a 50% decrease in PHQ score.

3.2.3 SECONDARY TRIAL OUTCOMES TO SUPPORT FUTURE IMPLEMENTATION

AIM 3: Analyses to support future implementation. Formative evaluation and cost analyses are conducted to support future implementation.

3.2.3.1 FORMATIVE EVALUATION OUTCOMES

Formative evaluation includes both qualitative and quantitative components to support future implementation.

Qualitative elements of formative evaluation will identify barriers and facilitators to implementing the intervention in this pragmatic trial. Weekly debriefs of NCMs, with research staff observing and taking field notes on all meetings, will be used to surface important issues. These will be used to populate a virtual white board with sticky notes and then code barriers and facilitators into domains including: the external environment, such as changes in the opioid epidemic, or waivers needed to prescribe buprenorphine; the MI-CARE intervention, such as issues with engagement of patients and primary care providers and their teams, or changes in standard care; patients and the health systems, such as characteristics of eligible patients and primary care teams and others in the health systems; and implementation and sustainment infrastructure, related to how the intervention is integrated into each organization in a sustainable manner, as in building EHR tools for NCM use. Our NCM team will also conduct chart reviews of all MI-CARE enrollees (usual care, invited to CC but not consented and consented, to find information that is not readily identifiable through EHR data pull, specifically qualitative information that contextualizes our study variables (see Chart Abstraction form). In addition, the team will conduct qualitative interviews with all staff delivering the MI-CARE intervention (NCMs) and OBAT nurses supporting treatment to better understand their experiences with the training and support on the MI-CARE intervention at both sites. See Supplement 4 for additional information outlining this process.

Quantitative elements of formative evaluation will be based on RE-AIM model (Reach, Effectiveness, Adoption, Implementation fidelity and Maintenance). Reach, adoption and implementation fidelity will be evaluated. (Effectiveness is evaluated as above in main aims, and Maintenance after the trial is beyond the scope of this study).

• Reach of the Intervention. We will evaluate the overall reach at the patient level - namely, demographic and clinical characteristics of those consenting for treatment and engaging in care contrasted to those invited but failing to consent/engage in care. Further, we will evaluate uptake of core component elements at the patient level including: NCM engagement, use of

measurement-based care, recommendations made to primary care provider, buprenorphine treatment for OUD, buprenorphine for pain, behavioral activation, specialty addiction treatment, and change in depression treatment. Each will be evaluated in the full intervention sample and in subgroups based on demographic and clinical characteristics (e.g., prior buprenorphine treatment, serious mental illness, prescribed opioids at baseline).

- Adoption of the intervention by primary care providers. We will evaluate measures of adoption at the primary care provider or team level: (e.g., buprenorphine treatment for OUD, buprenorphine treatment for pain, and change in depressive treatment).
- Implementation fidelity will be evaluated at the level of the NCM and the site, and will include evidence of NCMs consistent use of the core components of CC interventions (as described in Section 6.4.1.) such as: use of measurement based care, communication and/or coordination with patients' primary care teams (and, as appropriate specialists providing care), recommendation of evidence-based care for OUD and depression, and associated mental health and substance use conditions; use of BA for OUD and depression, and associated mental health and substance use conditions and attention to patient-centered care (e.g., engagement, and attention to other patient-prioritized conditions and concerns as appropriate).

3.2.3.2 OUTCOMES ASSOCIATED WITH NURSE CARE MANAGER INTERVENTION DELIVERY EFFORTS

We have built a REDCap enabled data collection system for the trial that allows time tracking to classify and quantify NCM efforts to deliver the MICARE study intervention (which includes all required elements of CMS specifications for reimbursable Psychiatric Collaborative Care Model [CoCM] services). Nurses track both time spent in direct patient treatment as well as coordinating relevant clinical services on the patients' behalf. Outcomes to be tracked include (per patient):

- CMS Billable NCM time supporting MI-CARE (CoCM services). We will identify the NCM time
 with patients delivering MICARE services as well as providing care coordination that is
 reimbursable under current CMS allowable payment to non-physician practitioners and
 specified in CMS published CPT codes and billing parameters.
- Additional (nonbillable) NCM time engaged in MI-CARE intervention activities. We recognize that the clinical complexity and high burden of social determinants of health in the study population of patients serviced by MI-CARE may result in the NCM spending either more time in CoCM billable activities than reimbursable currently by CMS as well as in supporting patient needs that may fall outside of currently allowable CPT codes. We will track non-billable time as well as billable time, therefore, to better characterize NCM total effort needed to support patients with OUD, depression, and frequent concomitant conditions using the CoCM model.

Finally, although it is beyond the scope of what can be accomplished within the allowable timeframe of the funded project, we have data available to determine the total cost of delivery of the intervention and the EHR data to determine the cost of medical care in each group at baseline and over follow-up by

broad setting (e.g., inpatient, emergency, outpatient, pharmacy) as well as important categories (e.g., behavioral health, etc.) thus allowing the possibility for a separately funded future study to examine cost effectiveness. Using the framework of cost-effectiveness, this would also allow the estimation of the incremental cost per additional day of OUD treatment (as described in Section 3.2.1. above), our primary outcome in the study.

3.3 OTHER TRIAL OUTCOMES RELATED TO OUD, DEPRESSION, PAIN, AND ADVERSE OUTCOMES

3.3.1 OTHER SECONDARY TRIAL OUTCOMES

3.3.1.1 BUPRENORPHINE TREATMENT AND/OR IMPROVED DEPRESSIVE SYMPTOMS

This composite identifies patients prescribed any buprenorphine—for OUD or pain—and/or who have documentation of clinically-significant improvement in depressive symptoms, as defined in Section 3.2.2. This composite is the most inclusive measure of benefit for depression, OUD, or improved safety for pain management with medications.

- **Treatment with buprenorphine** is a binary measure of treatment with buprenorphine formulations for OUD or pain defined as > 90 days of buprenorphine during the 12-month follow up period.³
- Clinically significant improvement in depressive symptoms is a binary measure of documented clinical response of depressive symptoms during follow-up (50% decrease in PHQ9 score or negative PHQ2 screen).

Rationale: Our preliminary research (see Supplement 2) revealed that many eligible patients may not accept both components of the intervention focused on OUD and depression. Some may not have OUD despite the ICD diagnosis in their record (e.g., due to incorrect or imprecise diagnosis coding), while for others with serious mental illness, their index PHQ (e.g., score 11) may already reflect optimal management from specialty mental health providers. Further, some patients with chronic pain who are prescribed opioids and may not believe they have an OUD, could benefit from a switch from prescribed opioids to buprenorphine for pain. There is increasing evidence on the benefits of buprenorphine for chronic pain and evolving strategies for switching to buprenorphine from a full μ -opioid receptor agonist for chronic pain management. ³¹⁻³³

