5 STUDY POPULATION

5.1 INCLUSION CRITERIA

Patients are identified up to weekly using an adaptive schedule at each site based on the routine assessment of study nurses' availability. For example, new sample may not be identified some weeks due to nurse out-of-office schedules, or to allow nurses to catch up if a previous week resulted in a large influx of new patients. Data extraction from each site's EHR and data systems is used to identify a sample cohort that meets criteria below. Data extraction may take several days to run against health system databases. Samples are randomized the same day that data extraction is completed. The "index date", Day 0, is the date of randomization.

Eligible patients must meet all 4 of the criteria below:

- (1) ≥1 in person or virtual encounter in a primary care setting in the 365 days prior to the data extraction start date at ≥1 primary care clinic.
- (2) Age ≥18 years on or before the data extraction start date.
- (3) ≥1 PHQ depression screening score of ≥10 in the 7 days prior to the data extraction start date.
- (4) Evidence of OUD in the 365 days prior to and including the date of the qualifying PHQ-9 score. Any 1 of the following qualifies as evidence of OUD:
 - ≥1 active OUD ICD-10 diagnosis code in any setting except labs and those covered by 42
 CFR Part II (see Section 5.2, Exclusion Criteria for more about 42 CFR Part II);
 - ≥1 prescription (orders or dispensed) for buprenorphine (oral formulations indicated for OUD, extended release injectable, and implant);
 - ≥1 procedure code for buprenorphine (oral formulations indicated for OUD, extended release injectable, and implant);
 - ≥1 ICD-10 codes for opioid overdose;
 - ≥1 OUD ICD-10 code, including remission, and prescription (orders or dispensed) or procedure code for injectable naltrexone.

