8.1.2 AIM 2 (SECONDARY) OUTCOME POWER

AIM 2: Improvement in depressive symptoms. Our Aim 2 outcome is a reduction in depressive symptoms from the study qualifying PHQ score to follow-up PHQ score documented as part of routine clinical care 3-13 months later.

Power calculations for Aim 2 estimate Minimal detectable difference (MDDs) that could be observed with 80% power, assuming a two-sided type 1 error rate of 0.05, under different scenarios regarding engagement (ranging from 30-50%). These calculations assume a 60% PHQ follow-up rate (among the initial sample of 800 patients) and standard deviation of 6.7 for the outcome, based on preliminary data from both study sites. Similar to Aim 1, the analysis for Aim 2 will adjust for the baseline value of the outcome (and potentially other baseline covariates). MDDs are also computed for a range of R² related to these prognostic variables, ranging from R² of 0 (corresponding to no prognostic covariates) to 0.4 (corresponding to more highly prognostic covariates). For engagement rates of at least 35%, or for lower engagement rates combined with highly prognostic baseline characteristics, the study sample size of 800 has sufficient power to detect a clinically meaningful difference of at least 5 for the outcome of change in PHQ, between baseline and intervention patients (and smaller in some scenarios). A prior study found a change between 2.59-4.78 to be the minimal clinically important difference (MCID), leading to a commonly defined threshold of 3-5 points for the MCID.

Table 8.1.2. Minimal detectable difference (MDD) in change in PHQ score, from baseline to follow-up, with 80% power comparing intervention versus control patients (intention-to-treat [ITT] analysis); and corresponding difference among engaged patients, across levels of engagement from 30-50%. MDDs are presented under different values of the R² of the included baseline covariates (e.g., baseline value of the outcome).

R ² of baseline	Mean change in in PHQ score, from baseline to follow-up						
covariate	ITT	Engaged patients (%) versus usual care					
		30%	35%	40%	45%	50%	
0	1.72	5.73	4.91	4.30	3.82	3.44	
0.1	1.62	5.40	4.63	4.05	3.60	3.24	
0.2	1.54	5.13	4.40	3.85	3.42	3.08	
0.3	1.44	4.80	4.11	3.60	3.20	3.08	
0.4	1.32	4.40	3.77	3.30	2.93	2.64	

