8.3.2 ANALYSIS OF THE SECONDARY DEPRESSIVE SYMPTOM OUTCOME

The powered secondary outcome is the change in PHQ score from baseline to follow-up (in the period 3-13 months after randomization). Following a similar approach as for the primary outcome, we will use a linear regression analysis of the change score (follow-up score minus baseline score), adjusted for the baseline score, health system, and other pre-specified covariates measured pre-randomization. From the regression model we will estimate the mean difference in the PHQ change score comparing patients randomly selected to be offered the CC intervention vs. the usual primary care control arm. Standard errors will be calculated using the robust (sandwich) variance estimator. The set of baseline variables that will be adjusted for will be selected using a parallel approach as for the primary outcome, prespecified in the standalone SAP.

Based on preliminary data, we expect that a subset of patients will have more than one follow-up PHQ (either PHQ-2 or PHQ-9) documented within the follow-up window. To determine our final approach to identifying which of these follow-up scores will be used, our biostatistical team will be conducting simulations to identify the most powerful analytic approach (from among all options considered that yield unbiased intervention effect estimates and correct type 1 error rates) using data from before randomization. Options that will be considered include selecting a single follow-up score (e.g., score documented closest to 12 months) and using all scores within the follow-up window and accounting for correlation of repeated measures within an individual. Additional details on the general simulation approach are provided in Supplement 3, part B, with full details and the final analytic approach to be specified in the standalone statistical analysis plan (SAP) for the trial.

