8.3.3 OTHER SECONDARY ANALYSES

Analyses of secondary outcome measures will follow the same general analysis approach as the primary outcome, applying a generalized linear model with appropriate outcome distribution and link function, and using a robust (sandwich) variance estimator. Secondary outcomes that are continuous measures (e.g., days of any medication treatment for OUD) will be analyzed using a parallel approach as for the primary and powered secondary outcome analyses. Models will adjust for health system and for the baseline value of outcome measures (if available), using the continuous version of binary measures where available (e.g., for clinically significant improvement in depressive symptoms we plan to adjust for the baseline PHQ score). Other pre-selected covariates to be adjusted for in the models will be identified using a similar approach as for the primary outcome, pre-specified in the standalone SAP. For binary

secondary outcomes (e.g., sustained buprenorphine treatment for OUD, clinically significant improvement in depressive symptoms), we plan to use a modified Poisson regression with robust variance to estimate a relative rate. For the secondary composite measure of any major adverse event (including opioid OD, other drug OD, suicide attempt or other self-harm, hospitalizations, or death) during the follow-up period, we will apply survival analysis methods for time-to-event data (i.e., time to the first major adverse event). Patients are censored at 12 months (end of follow-up) or disenrollment from the health system (for one of the sites with enrollment information available). Kaplan-Meier curves will be generated and Cox proportional hazards models stratified by health system will be used to estimate hazard ratios. In addition, we may also consider covariate-adjusted estimators for time-to-event outcomes that can improve precision and power⁴⁵, such as the targeted minimum loss-based estimator of the difference in restricted mean survival times (RMSTs) at 12 months between intervention and control groups. The final analytic approach will be specified in the standalone SAP for the trial.

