13.1.1 RETROSPECTIVE COHORT ANALYSIS

Before and during the trial, a secondary dataset—with data from before the start of the trial—is used to conduct quality checks on programming code and perform necessary simulations. This will be a retrospective cohort of KPWA and IUH patients meeting trial inclusion criteria over a 25-month period prior to randomization, with data collected during a 4-year period including 2 years prior to the sample eligibility period. Specifically, this retrospective cohort analysis will be used for two key data and analytic quality purposes:

To allow quality assurance on our computer code for final trial sample specifications, and final
outcome measures and covariates for the main trial, including data coding, cleaning and quality
checks. Based on preliminary analyses, the ongoing pilot study, and new results in the publish
literature, refinements have been made to inclusion and exclusion criteria, and measure
specifications, which necessitate this important quality assurance work.

- To perform modeling that will inform final statistical approaches. This includes simulations on a sample that had an index PHQ-9 of 10 or more between over a 1-year period and allows covariate data from 2-years prior to index PHQ-9 score, and follow-up data over the 13 months after the index PHQ score. Simulations will address covariates to adjust for in primary analyses to improve power (Aim 1). These are described fully in Supplement 3. Additional simulations address which follow up PHQ-2 or PHQ-9 score to use if patients have multiple, only PHQ-2, or no follow-up scores in the 12-month window (Aim 2).
- Refining/debugging of code for main analyses before trial outcomes data are available.

These activities are intended to allow coding and rapid analysis of final trial data during the 2 months after complete trial data become available (April-May 2024).

An additional waiver of consent and HIPAA is sought from the IRB to collect and utilize these data for the purposes stated above.

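### The negative-PHQ-2 route to depression response has no baseline condition, so a patient already PHQ-2-negative at entry can count as a responder without any change

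*Protocol*

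**What the plan says.** - **Entry.** Section 5.1 asks for "≥1 PHQ depression screening score of ≥10 in the 7 days prior to the data extraction start date". The next criterion calls this the qualifying PHQ-9: "Evidence of OUD in the 365 days prior to and including the date of the qualifying PHQ-9 score". Nothing is required of the first two items.
- **Response.** Section 3.3.1.1 gives the binary depression component of its composite as "documented clinical response of depressive symptoms during follow-up (50% decrease in PHQ9 score or negative PHQ2 screen". It states no PHQ-2 cut-off.
- **The definition it refers to.** Section 3.3.1.1 points to Section 3.2.2, which reads "clinically significant improvement in depressive symptoms defined as at least a 50% decrease in PHQ score". There is no PHQ-2 route there.
- **PHQ-2 at follow-up.** Section 8.3.2 expects some patients to have "more than one follow-up PHQ (either PHQ-2 or PHQ-9) documented within the follow-up window".
- **Analysis.** Section 8.3.3 uses modified Poisson regression to estimate a relative rate for binary secondary outcomes, and adds that "for clinically significant improvement in depressive symptoms we plan to adjust for the baseline PHQ score".

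**The concern.** The two routes to response are of different kinds. A 50% fall in PHQ-9 measures change from entry. A negative PHQ-2 describes where the patient is at follow-up and says nothing about where the patient started. Eligibility rests on the nine-item total, which the other seven items can carry, so an eligible patient may satisfy the second route on the day of the qualifying questionnaire.

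Such patients occur in both arms and count as responders whether or not the offer of collaborative care helps. They raise the response rate and pull the relative rate toward 1, both for the depression measure alone and for the composite. The label of clinically significant improvement is then not accurate for them. Baseline adjustment does not cure this, because it does not change who is classed as a responder.

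**Working it through.** **Stated figures.** The protocol gives no response rate, effect size or power for this measure or its composite, so there is nothing to reproduce. The nearest figure is the ITT detectable difference of 1.72 in Table 8.1.2. Section 8.1.2 says "These calculations assume a 60% PHQ follow-up rate (among the initial sample of 800 patients) and standard deviation of 6.7", so there are 0.60 × 800 / 2 = 240 per arm, and (1.960 + 0.842) × 6.7 × √(2/240) = 1.71. That figure stands and is not in question.

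**Assumptions not in the protocol.** The PHQ-9 is nine items scored 0-3. The PHQ-2 is its first two items. Negative means a sum of 2 or less, with 1 or less as the alternative.

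**Step 1: can it happen?** Let items 1-2 sum to 2 and the other seven sum to 8. The total is 10 (eligible) and the PHQ-2 is 2 (negative). Identical answers at follow-up give a PHQ-9 change of 0%, yet the PHQ-2 route is met. Totals from 10 to 2 + 21 = 23 are compatible with a negative PHQ-2. Going from items 1-2 = 0 and total 10 to items 1-2 = 2 and total 23 is a worsening that also qualifies. Of the 231,182 item patterns with total 10 or more, 76,172 (32.9%) are PHQ-2-negative at 2 or less, and 34,796 (15.1%) at 1 or less. These count possible patterns and are not a prevalence.

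**Step 2: how often, under a model?** The model is one-factor ordinal, with loadings 0.6, 0.7 or 0.8 and item thresholds (-0.5, 0.5, 1.1) or (-1.0, 0.0, 0.7). The entry-to-follow-up factor correlation is 0.6 or 0.75, with no mean shift. Patients are conditioned on an entry total of 10 or more and are all read on the PHQ-2 at follow-up. Ranges run over the 12 settings.

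| Share of patients read on the PHQ-2 | Negative at ≤2 | Negative at ≤1 |
|---|---|---|
| Already PHQ-2-negative at entry | 18-32% | 3-11% |
| PHQ-2-negative at follow-up, no 50% PHQ-9 fall | 16-32% | 4-13% |
| As the row above, and already negative at entry | 4.9-12.1% | 0.3-1.9% |
| Already negative at entry, negative at follow-up, total no lower than at entry | 1.5-4.0% | 0.1-0.5% |

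The third row is the mechanism at issue. The fourth is its strictest form.

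**Step 3: points added to the response rate.** The share of follow-ups read on the PHQ-2 is not in the documents; 20-50% is assumed.
- Cut of 2 or less: 0.20 × 4.9 = 1.0 to 0.50 × 12.1 = 6.1 points. With no fall in total: 0.20 × 1.5 = 0.3 to 0.50 × 4.0 = 2.0 points.
- Cut of 1 or less: 0.20 × 0.3 = 0.06 to 0.50 × 1.9 = 0.95 points.

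**Step 4: effect on the relative rate.** Take an assumed true response of 25% against 20%, a ratio of 1.25, and add the same points to each arm.
- 1 point: 26/21 = 1.24.
- 6 points: 31/26 = 1.19.
- 0.3 points: 25.3/20.3 = 1.25.
- 2 points: 27/22 = 1.23.

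**The case against.** **Size is unknown.** The cut-off, the item make-up, the model and the PHQ-2 share are all assumed. If a site gives the PHQ-9 only after a positive PHQ-2, few patients would be negative at entry. The protocol neither states nor excludes such a rule. This limits the size of the point; the flaw in the wording remains.

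**Left to the SAP.** Section 13.1.1 says "Additional simulations address which follow up PHQ-2 or PHQ-9 score to use if patients have multiple, only PHQ-2", and Sections 3.2.2 and 8.3.2 also defer the choice among follow-up scores. Those deferrals concern the Aim 2 change score. The responder rule is already written out in Section 3.3.1.1.

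**It may vanish on reconciliation.** If Section 3.3.1.1 is brought into line with Section 3.2.2, the PHQ-2 route goes and the problem with it. That is correct, and the fix starts there.

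**Low stakes.** The measure is an unpowered secondary outcome and one arm of an and/or composite meant to be inclusive. This stands.

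**Stronger readings to avoid.** A reader might treat every patient who is PHQ-2-negative without a 50% PHQ-9 fall (16-32%) as a false responder, which at a 20-50% PHQ-2 share gives about 3-16 points. That is not supported. In the model, roughly 61-70% of them moved from PHQ-2-positive to PHQ-2-negative at a cut of 2 or less, a real change on the screen. A reader might also infer a spurious benefit. Responders added equally to both arms dilute the ratio, and the documents do not establish that the share differs by arm.

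**Conclusion.** The point holds as a defect of definition. Section 3.3.1.1 lets an eligible patient meet clinically significant improvement with no change, and Section 3.2.2, its own reference, does not contain that route. This follows from the text once the PHQ-2 is taken as two items of the PHQ-9, and it holds at both cut-offs examined.

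The consequence is modest: dilution toward 1 of the relative rate for one secondary responder measure and the composite that includes it. With a cut of 2 or less and 20-50% of follow-ups on the PHQ-2, about 1-6 points of response are unrelated to change of the required size, of which 0.3-2 points are patients with no fall in total. At a cut of 1 or less it is under 1 point. These sizes rest on the assumed item model and PHQ-2 share, and the trial's own share cannot be found from the protocol. Days of buprenorphine treatment and the powered PHQ change score are not affected.

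**What to change.** Reconcile Sections 3.3.1.1 and 3.2.2 so that both carry one rule:

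1. Where a follow-up PHQ-9 exists, only the 50% decrease on the PHQ-9 decides response.
2. A negative PHQ-2 counts as response only when the follow-up is PHQ-2 only and items 1-2 of the qualifying PHQ-9 were a positive PHQ-2. State the cut-off and use the same one at both times.
3. PHQ-2-only patients who were already negative at entry do not meet the depression component through the PHQ-2. Handle them under the plan's approach to missing PHQ data, with a sensitivity analysis counting them as non-responders. They can still meet the composite through buprenorphine.

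The cost is a sentence or two in the protocol and SAP, plus extraction of items 1-2 from the qualifying PHQ-9. The protocol does not say these item scores are extracted, so their availability at both sites should be confirmed. The response rate will be lower. Step 3 also loses a little depression information in a trial that already expects only 60% PHQ follow-up, which is why those patients should stay in the analysis and not simply be dropped as not assessable.
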